ReOpening Schools Safely and Educating Youth (ROSSEY Study) – Early Learning Ancillary Study

Clinical Trials.gov : NCT05965323

June 30, 2022

STATISTICAL ANALYSIS PLAN

1. Introduction to the SAP

This statistical analysis plan (SAP) describes the plans for statistical analyses that will address the study's protocol objectives.

2. Study Schema and objectives

Purpose:	Evaluate if risk communication health education can increase uptake of COVID-19 mitigation measures, improve children's school attendance, and increase families' physical and mental well-being using a single-arm pre/post study.
Design:	A single-arm pre/post-study
Central Hypotheses:	Our central hypotheses are that students and parents who view the risk communications will be more likely to have increased COVID-19 testing and vaccine uptake.
Primary Objectives:	
• To determine if implementing three COVID-19 education comic books for children and two COVID-19 education videos for parents will increase COVID-19 testing and vaccine uptake in children.
Secondary Objectives:	
• To determine if implementing three COVID-19 education comics books for children and two COVID-19 education videos for parents will increase physical activity, improve sleep, increase emotional regulation in children.• To determine if implementing three COVID-19 education comics books for children and two COVID-19 education videos for parents will increase physical activity, improve sleep, decrease depression and anxiety in parents
Population:	Children ages 3-5 enrolled in the Early Learning program in Yakima School District
Study Size:	Early Learning is an ancillary study with no defined sample size. We will enroll and recruit participants for a total of eight weeks
Primary Outcome Measurements:	
A. COVID-19 testing data available through self-reported surveyB. COVID-19 vaccine data available through self-reported survey
Study Duration:	11 months – September 2022- August 2023

3. Study Design

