The ancillary study runs parallel with the larger ROSSEY RCT. Recruitment, enrollment, and baseline assessment are expected to last two months (September-November 2022). Enrolled participants will not receive the comic book and parent video series until after completion of the ROSSEY RCT Post 1 follow-up Survey to not bias the data of older siblings participating in the ROSSEY RCT. A follow-up assessment for Early Learning participants is anticipated to take place 10 months after the launch of recruitment (July-August 2023)

4. Sample size and power

Early Learning is an ancillary study of 50 participants. We will enroll and recruit participants for a total of eight weeks.

Enrollment Criteria

Parent/Guardian eligibility criteria for participation in the study include:

- Must have a child attending the Early Learning Program in the Yakima School District
- Must be able to provide informed consent and legal guardian assent either virtually, on the telephone, or in-person.
- Must have a permanent mailing address available for study staff to mail necessary materials OR a working email address.

5. Population and Data Source

Participants enrolled in the ROSSEY Study: 50 children and parents from the Yakima School District. Any participants subsequently found to be ineligible will be removed. The data sources for the primary analyses are COVID testing results received from the school administration and the survey data as entered in REDCap. The COVID vaccination status data is obtained through the parent and child surveys, completed in REDCap.

6. Presentation of analyses

For each of the continuous outcomes (including the primary outcome), the mean and standard deviation will be presented pre/post intervention and p value. For binary outcomes, the percentage and frequency of children in the outcome category of interest (e.g., percentage vaccinated) will be presented pre/post and p value.

7. Outcome Definitions

a. Primary Outcomes

The two co-primary outcomes of the trial are COVID-19 testing and COVID-19 vaccine uptake. COVID-19 data are captured through school testing and self-reported survey, and COVID-19 vaccine uptake data are captured through self-reported survey. All children and parent data will be included in the intention-to-treat analysis.

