COVID-19 testing: Health reports from the school are provided for the 2022-2023 school year that list positive covid test results of study participants with the date of testing and the school of attendance. Positive test results for COVID will be a binary, yes/no variable.

COVID-19 vaccine uptake: Parents are asked at enrollment to report their vaccination status and their child's vaccination status. At post survey, the parent is asked to report if they or their child have received any COVID-19 vaccine or booster since enrollment. Vaccination status will be a binary, yes/no variable.

b. Secondary Outcomes

Secondary outcomes for the trial include the following outcomes from the PROMIS – Pediatric and Parent Proxy Instruments. The PROMIS instruments used are Children's physical activity (PA), sleep, stress, depression, and anxiety. Parents' PA, sleep, stress, depression and anxiety. The final score is represented by the T-score, a standardized score with a mean of 50 and a standard deviation (SD) of 10.

The outcome measures will be collected at pre-and post-assessment.

8. Primary exposure definition

Receiving the educational materials: three comic books and two graphic motion videos.

9. Interim analysis plan

For this study, there was no interim analysis.

10. Multiple testing

We will adjust for multiple testing by controlling FDR.

11. Missing Data

We will inspect missing data mechanisms and the amount of missing data. We will conduct an additional sensitivity analysis with multiple imputations using multivariate imputation with chained equations (MICE) approach. We will report the amount of missing data and apply appropriate methods to account for the missing data.

12. Planned Statistical Analyses

a. Baseline Demographics

The baseline characteristics of enrolled participants will be summarized in a table.

b. Efficacy Analyses Overview

Pre/post-survey outcome analyses will be conducted after all participants have been contacted and the survey is closed with missing responses marked as loss to follow-up.

- 1) **Descriptive Analyses:** Positive COVID test results will be summarized by counts. Vaccine status and COVID testing results will be presented as counts and percentages. Continuous variables will be summarized by mean, standard deviation (SD), and median (IQR). Secondary outcomes will be compared using Chi-squared tests.

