- 2) **Primary Objectives:** The primary analysis of vaccine uptake and COVID testing will be conducted using a chi-squared test using $\alpha = 0.05$ and report pre/post changes over time.
- 3) **Secondary outcomes:** The secondary outcomes for the trial include measures from the PROMIS – Pediatric and Parent Proxy Instruments. The PROMIS instruments used are children's PA, sleep, stress, depression, and anxiety and parents' PA, sleep, stress, depression, and anxiety.

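### The single-arm pre/post test of vaccination status cannot show that the materials increased uptake, whether the undefined post status is cumulative or limited to doses since enrolment

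*SAP*

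**What the plan says.** SAP 2 describes the design as "a single-arm pre/post study" and words the primary objective causally: whether three comic books and "two COVID-19 education videos for parents will increase COVID-19 testing and vaccine uptake in children".

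SAP 7a defines the vaccine co-primary from two different survey items. At baseline, "Parents are asked at enrollment to report their vaccination status and their child's vaccination status". At follow-up, "the parent is asked to report if they or their child have received any COVID-19 vaccine or booster since enrollment". It then adds: "Vaccination status will be a binary, yes/no variable". It gives no rule for combining the two items into a post value.

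SAP 6 says that for binary outcomes "the percentage and frequency of children in the outcome category of interest (e.g., percentage vaccinated) will be presented pre/post and p value". SAP 12b(2) gives the test, at alpha 0.05: "The primary analysis of vaccine uptake and COVID testing will be conducted using a chi-squared test". SAP 10 adds FDR control without naming the family of tests.

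On timing, Protocol I and SAP 3 put baseline in September-November 2022 and follow-up in July-August 2023. Both hold the materials back until an assessment in the parent RCT is finished. Protocol VI (Risk Communication) dates that assessment, and so the distribution, to about December 2023, and starts follow-up contact 6 weeks after distribution.

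The documents give no baseline vaccination rate, no expected background uptake and no comparison group for this study. They do not limit the outcome to doses received after the materials were sent.

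**The concern.** Having ever been vaccinated is a one-way state: a child can enter it but not leave it. If post status is cumulative, the tested null of equal percentages at the two surveys is false as soon as one child is vaccinated for any reason. This goes further than the usual caveat about uncontrolled pre/post studies. A PROMIS score can drift either way without an effect, but cumulative vaccination can drift only upward, which is the direction the hypothesis predicts.

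The recall period adds to this. It starts at enrolment, while the materials are sent much later, so doses that they could not have influenced count as post-intervention uptake.

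At stake is a co-primary result that would be reported as showing that the comics and videos raise vaccine uptake, when it shows only that some children were vaccinated between two dates.

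**Working it through.** **Inputs from the documents.** N = 50 (SAP 4 and 5; SAP 2 and Protocol IV say there is no defined size). Chi-squared test, alpha 0.05 (SAP 12b). Items as in SAP 7a. Dates as above. The plan states no power, effect size or vaccination rate, so there is no figure of its own to reproduce.

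**Assumptions.** Complete follow-up, no effect of the materials, two-sided test, Pearson statistic without continuity correction, no FDR adjustment. Let b be the number vaccinated at baseline, and q the background uptake, that is, the share of the other 50 − b children who are vaccinated between surveys. The values of b and q are assumed.

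**1. Cumulative coding.** The comparison is b/50 against (b + k)/50, where k ~ Binomial(50 − b, q). First find the smallest k that gives p < 0.05, then compute P(K ≥ k). For b = 10, k = 8 gives chi-squared 3.17 (p = 0.075) and k = 9 gives 3.93 (p = 0.047), so 9 are needed.

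| Baseline | Smallest k | q = 5% | 10% | 15% | 20% |
|---|---|---|---|---|---|
| 0% (b = 0) | 4 | 24% | 75% | 95% | 99% |
| 10% (b = 5) | 8 | 0.2% | 8% | 36% | 70% |
| 20% (b = 10) | 9 | <0.1% | 1.5% | 14% | 41% |
| 40% (b = 20) | 10 | <0.1% | <0.1% | 1% | 6% |

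The chance of any observed rise is 1 − (1 − q)^(50 − b). At its lowest in this grid (b = 20, q = 5%) it is 1 − 0.95^30 = 79%. For b = 10, q = 20% it exceeds 99%.

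**2. A paired test does not help.** With one-way changes only, exact McNemar gives 2 × 0.5^5 = 0.0625 for 5 conversions and 2 × 0.5^6 = 0.031 for 6, so 6 suffice at any baseline. For b = 10, q = 20% the chance of significance rises from 41% (Pearson) to 84%.

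**3. Literal coding.** Suppose 20/50 were ever vaccinated at baseline and 8/50 report a dose since enrolment. The figures go from 40% to 16%, chi-squared = 7.14, p = 0.008: a significant fall, although eight children received a dose.

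**4. Exposed share of the recall period.** Take six exposed weeks, from distribution to the start of follow-up contact.
- Follow-up in July-August 2023: the period runs from 30 weeks (30 November 2022 to 1 July 2023) to 52 weeks (1 September 2022 to 31 August 2023). 6/52 to 6/30 is about 12% to 20%.
- Distribution in December 2023: from 58 weeks (30 November 2022 to 12 January 2024) to 82 weeks (1 September 2022 to 31 March 2024, an assumed last date). 6/82 to 6/58 is about 7% to 10%.

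Twelve exposed weeks would double these shares. In all four cases most of the period precedes the materials.

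**The case against.** **The SAP never says that post status is cumulative.** This stands. The phrase about percentage vaccinated in SAP 6 favours that reading but does not settle it. A reader might infer that the percentage can only rise however the follow-up item is coded. The documents do not support that: step 3 shows a fall under literal coding, and loss to follow-up in an unpaired comparison could also lower the post percentage.

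**A significant result is not inevitable.** This stands too. A reader might infer that the plan will produce a false claim of benefit. With a non-zero baseline, the planned test gives anything from under 0.1% to 70% in the grid above. The high figures at low uptake come from assuming that no child was vaccinated at enrolment, which the documents do not say.

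**FDR control is planned.** It lowers the figures. If the working threshold were 0.025 (two co-primaries, the other null), 11 conversions would be needed at b = 10, and the 41% would become 16%. It does not remove the problem, because adjusting a p value does not separate the materials from background uptake.

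**The design is openly declared as single-arm.** True, and weak attribution comes with it. But the objective in SAP 2 is causal and a p value is attached to it, and the SAP nowhere limits what a rise may be taken to mean.

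**A before/after dose-rate comparison is also uncontrolled and weak.** This stands. Assume 20% uptake before mailing, so 50 × −ln(0.8) = 11.2 expected doses, over 8 to 12.5 months, with 1.4 months after mailing. A true doubling would give 2 × 11.2 × 1.4/8 = 3.9 or 2 × 11.2 × 1.4/12.5 = 2.5 later doses, and exact power of about 17% to 23%. It therefore belongs as a supportive analysis, not as a replacement co-primary.

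**Conclusion.** The concern holds in conditional form. SAP 7a leaves post vaccination status undefined. Under cumulative coding, background uptake alone produces a rise; under literal coding, pre and post are not the same variable. Under either, the chi-squared test cannot show that the materials increased uptake, and the item counts doses given before they were sent.

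Under cumulative coding, the chance of wrongly crediting the materials is set by baseline coverage and background uptake, not by alpha. The range of under 0.1% to 99% rests on the assumptions listed in the working, since the documents supply no rates.

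The SAP sentence that names the test also covers COVID-19 testing. A reader might extend the argument there, but testing is recorded as positive school results and is not a cumulative status in this sense. The point is limited to vaccination.

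**What to change.** 1. **SAP 7a:** define post vaccination status explicitly, and add the month of each child dose to the follow-up item, so that doses before and after the mailing date can be separated.
2. **SAP 6 and 12b(2):** report percentage vaccinated pre and post as description, with a confidence interval and no p value. **SAP 2:** state that a rise in this percentage is not evidence that the materials increased uptake.
3. **SAP 12b:** add, as a supportive analysis, the within-child rate of new doses after against before mailing, with an exact interval. State its limits: few events, recall error, fewer unvaccinated children left in the later period, and residual calendar effects.
4. **Protocol I and VI, SAP 3:** reconcile follow-up in July-August 2023 with distribution around December 2023. If both stood, follow-up would precede the materials and there would be no post-mailing period to analyse.

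The cost is one survey field and some SAP wording. Parents must recall the month of a dose, the interval for the rate ratio will be wide, and the vaccine objective becomes largely descriptive.

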The ancillary study runs parallel with the larger ROSSEY RCT. Recruitment, enrollment, and baseline assessment are expected to last two months (September-November 2022). Enrolled participants will not receive the comic book and parent video series until after completion of the ROSSEY RCT Post 1 follow-up Survey to not bias the data of older siblings participating in the ROSSEY RCT. A follow-up assessment for Early Learning participants is anticipated to take place 10 months after the launch of recruitment (July-August 2023)

II. Aim 1

Evaluate if risk communication health education can increase uptake of COVID-19 mitigation measures, improve children's school attendance, and increase families' physical and mental well-being using a single-arm pre/post study.

III. Study Population

We will collaborate with the Yakima School District to recruit Early Learning students (3, 4 and 5 years old) and their parent or Guardian(s) into the research study. We will recruit Early Learning students into the study regardless of their participation in SARS-CoV-2 testing provided by the Yakima School District. This will allow us to evaluate the effect of the risk communication strategies on the uptake of SARS-CoV-2 testing and other mitigation measures.

IV. Sample Size

Early Learning is an ancillary study with no defined sample size. We will enroll and recruit participants for a total of eight weeks.

V. Enrollment Criteria

Parent/Guardian eligibility criteria for participation in the study include:

- Must have a child attending the Early Learning Program in the Yakima School District
- Must be able to provide informed consent and legal guardian assent either virtually, on the telephone, or in-person.
- Must have a permanent mailing address available for study staff to mail necessary materials OR a working email address.

VI. Study Procedures

Recruitment, Screening and Consent

Enrollment and recruitment of the Early Learning ancillary study will start the second academic year of the RCT (2022-2023). Study information in the form of a flyer will be sent home with students to parents through school email by the principal and posted on the school Parent Square site in September of 2022. In addition, ROSSEY staff will attend the Early Learning Open House to hand out study information and obtain the phone number or email address of interested parents. ROSSEY staff will follow up with interested parents and provide further information about the study.

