Risk Communication: Risk communication, in the form of comic books with accompanying read-along videos for the children (n=3) and videos for the parents (n=2) will be distributed in English and Spanish to all enrolled students within two weeks of completion of the ROSSEY RCT final assessment (December 2023). Three comic books will be distributed by mail and parents will be sent a password-protected link with the mailed comic to access the parent videos and comic book read-along videos. All intervention materials (i.e., children's comic books and parent videos) will be distributed after the final assessment of the larger ROSSEY RCT study is complete. The delay is to eliminate possible contamination of the RCT by siblings of comparison students who will receive the comic books as part of this ancillary study.

Outline of Early Learning Study Procedures

Follow-up Survey: We will contact parents 6 weeks after the risk communication intervention distribution. Parents will be asked to complete the follow-up survey either online or by phone. The surveys will ask for updates to their contact and demographic information, child's COVID-19 vaccination status, and child's SARS-CoV-2 mitigation behaviors and the secondary outcome measures.

Following the protocol from the ROSSEY RCT, the post assessment will take place over 6 weeks, allowing two weeks for final contact prior to closure. For EL participants with missing or phone numbers no longer in service, ROSSEY staff will contact the YSD to 1) determine if the student is still attending YSD, 2) find out school and teachers name to send a notice through the school to the parent letting them know we are trying to reach them. Students determined to still be enrolled at YSD, and are non-responders to the follow up survey, will receive an at home visit by ROSSEY staff as a final attempt to reach student and parent to complete survey. Follow-up assessment closure will take place one week after completion of home visits.

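### The COVID-19 testing co-primary is compared pre with post without any observation window, so unequal windows alone can produce a significant result in either direction

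*SAP*

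**What the plan says.** COVID-19 testing is one of two co-primary outcomes (SAP 7a). Its data come from the parent survey (SAP 2) and also from the school (SAP 5 and 7a). The school reports cover the 2022-2023 school year and are reports "that list positive covid test results of study participants with the date of testing and the school of attendance". The variable is then collapsed: "Positive test results for COVID will be a binary, yes/no variable".

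SAP 12b item 2 sets the analysis: "The primary analysis of vaccine uptake and COVID testing will be conducted using a chi-squared test", at a 0.05 level, and the team will "report pre/post changes over time". No exposure time enters.

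For vaccination, SAP 7a describes a question at enrollment and a follow-up question covering the time from enrollment onward. For testing it describes neither a baseline question nor a recall period. Protocol VI says that baseline uses the main trial's survey, and still holds a placeholder where the baseline survey should be described.

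On timing, Protocol I and SAP 3 put baseline in September-November 2022 and follow-up in July-August 2023. Protocol VI (Risk Communication) puts distribution of the materials around December 2023. Under Follow-up Survey it adds: "We will contact parents 6 weeks after the risk communication intervention distribution".

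**The concern.** A status on a given date, such as being vaccinated, can be compared at two dates. Whether a child has had a test event cannot be compared in that way unless both periods have the same length, because the chance of a yes rises with every week observed. A chi-squared test on two such percentages has no means of telling more testing from more time.

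If the windows differ, a co-primary result may be significant when the materials do nothing, and the sign depends on which window is longer. Because the plan leaves the windows open, they could be chosen after the data are seen, and the sign with them. This is separate from the school reports ending with the 2022-2023 year: it would remain if those reports were extended or if the survey supplied all post data.

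**Working it through.** **Inputs from the documents.** 50 children (SAP 4 and 5; SAP 2 and Protocol IV say that no size is defined). Chi-squared at 0.05. Recruitment from September 2022. First follow-up contact 6 weeks after mailing, a 6-week assessment period, and closure one week after home visits (Protocol VI), so a late response may come at about 6 + 6 + 1 = 13 weeks.

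**Assumptions.** First of the month where only a month is given. Two-sided, uncorrected Pearson test. A constant weekly chance *h* of a recorded event, 0.25% to 0.5%, because the documents give no rate. Pre and post treated as independent, as the named test does.

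**1. The plan's own figures.** The 50 cannot be reproduced, since no power, effect or rate is stated. The calendar in Protocol I can be: September 2022 plus 10 months is July 2023, as written.

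**2. Windows if the split is at mailing.**
- Follow-up on 1 July 2023 less 6 weeks puts mailing at 20 May 2023. From 1 September 2022 that is 261 days, or 37.3 weeks.
- Mailing on 1 December 2023 is 456 days, or 65.1 weeks.
- Post of 6 weeks: 37.3/6 = 6.2 and 65.1/6 = 10.9. Post of 13 weeks: 37.3/13 = 2.9 and 65.1/13 = 5.0.

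Pre is therefore about 3 to 11 times longer.

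**3. Windows if testing followed the vaccine wording.** Enrollment between 15 September and 30 November 2022, with follow-up between 1 July and 31 August 2023, gives a post period of 30.4 to 50.0 weeks. With an assumed 4-week baseline look-back and 45 weeks of post, post is 45/4, or about 11 times longer.

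**4. Chance of a yes with no effect.** P = 1 − (1 − h)^weeks. At 0.5%, for example, 1 − 0.995^38 = 17.3% and 1 − 0.995^6 = 3.0%. The 37.3 weeks are rounded up to 38.

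**5. How often the planned test rejects.** For x and y yeses out of 50, chi-squared = 100·[x(50−y) − y(50−x)]² / [50·50·(x+y)·(100−x−y)]. The exact binomial probabilities are summed over all tables where this exceeds 3.841.

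| Pre v post (weeks) | h per week | P pre v P post | Rejects with no effect | Apparent direction |
|---|---|---|---|---|
| 38 v 6 | 0.25% | 9.1% v 1.5% | 39% | fall |
| 38 v 6 | 0.5% | 17.3% v 3.0% | 71% | fall |
| 38 v 13 | 0.25% | 9.1% v 3.2% | 21% | fall |
| 38 v 13 | 0.5% | 17.3% v 6.3% | 42% | fall |
| 4 v 45 | 0.5% | 2.0% v 20.2% | 89% | rise |

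With Yates correction, the same sum at 0.5% gives 55%, 27% and 79% for 38 v 6, 38 v 13 and 4 v 45 weeks; 38 v 6 at 0.25% gives 17%.

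As single results at 0.5%, rounded expected counts of 9 v 1 (38 v 6 weeks) give p = 0.008, and 9 v 3 (38 v 13 weeks) give p = 0.06.

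**6. Equal windows.** With the same probability in both periods, between 5% and 50%, the test rejects in 4.3% to 5.7% of trials. The excess disappears.

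**The case against.** The strongest reply is that the documents never say that pre runs from September 2022 to mailing. Pre may simply be the baseline survey. That instrument comes from the main trial and is not in these documents, so it may set a recall period for testing. This stands as a limit on what can be claimed about the survey. It does not supply a window for the dated school events, nor does it show that any survey window matches between the two assessments.

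A reader might infer that the plan's own dates make pre 6 to 11 times longer than post, so that the result simply measures window length. The documents do not support that. The ratio needs a split at mailing and a post period of exactly 6 weeks, and its two ends come from two calendars that conflict. A 13-week post period lowers it to about 3 to 5, and the wording used for vaccination reverses it.

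The weekly rates are also assumed, and at low rates the distortion is modest: if the chance of a yes in the longer window is only 5% and the ratio is 6.2, the test rejects in about 16% of trials, or 3% with Yates correction. Finally, 65 weeks to December 2023 includes a summer and months that the school reports do not cover, so a constant rate is doubtful there. None of the rejection rates above uses that window.

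**Conclusion.** The concern holds in this form: the testing co-primary is an ever/never variable built from accumulating events, compared pre with post with no window, cut date or person-time. Each split considered here, drawn from the stated dates, is unequal, but its size and direction cannot be determined from the documents.

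Under no effect, the false-positive rate of a nominal 5% test is then about 39% to 71% for 38 v 6 weeks, about 42% for 38 v 13 weeks at the higher rate, and about 89% in the opposite direction for 4 v 45 weeks at that rate. These figures rest on 50 children at both times, a constant assumed weekly rate, an uncorrected test and independence of the two periods. The supportable statement is that window length *can* drive this co-primary result. That is more than a missing detail, because following the plan as written can yield a significant finding of either sign with no effect.

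**What to change.** In SAP 7a and 12b:

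- Define the testing outcome on pre and post windows of equal length (for example 42 days) anchored to the mailing date, with the same cut for every child whenever the survey is answered. Alternatively, compare tests per child-week with a log person-time offset and allowance for clustering within child.
- Take any test, and its date, from the survey, with the same recall period at both assessments. A window directly before mailing falls after baseline closes, so the follow-up survey would have to ask about dates on both sides of mailing.
- Use the school list only for positive results, and only for weeks that it covers in both windows. It cannot supply negative tests, nor windows around a December 2023 mailing.
- Reconcile the July-August 2023 follow-up with the December 2023 distribution, so that the windows can be placed.

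The cost is SAP wording, one survey date item and few counted events. At 0.5% per week a 42-day window expects 50 × 3.0%, or about 1.5, children with an event. The chi-squared test then has about 9% power for a doubling of the weekly rate and 21% for a tripling. The testing comparison will be imprecise and should be reported with a confidence interval.
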